8.4 Schedule for Additional 5 Control HIV Uninfected Subjects (n=5)

Our first experiments with human tissue demonstrated that we need to change procedures for handling and imaging the tissue. The first few controls were not fully interpretable because of this. In addition the data we are generating suggests that increasing the number of controls by 5 subjects will significantly increase our power to detect changes in the FRCn attributable to the intervention.

8.4.1 Screening

At this visit, consents will be reviewed in detail and the subject will have the opportunity to ask any questions they may have. The designated study staff or physician will interview the participant and a physical exam will be performed. Blood will be obtained for HIV antibody, liver function tests, electrolyte panel including creatinine, and CBC. Screening for hepatitis C will also be performed. Women of childbearing age will have a urine pregnancy test. Once lab results are available (within 3 days), they will be reviewed by designated study staff to ensure that laboratory inclusion/exclusion criteria are met. If the subject has met all entry criteria, they will be contacted by the designated study staff. The study protocol will again be reviewed and if the subject is still interested in enrolling, they will be scheduled for the study visit. Subjects who have not met the criteria will also be contacted by the designated study staff and told that they do not qualify to participate in the study

8.4.2 MRI Sub-Study

Within two weeks of the biopsy a MRI will be scheduled, see Appendix I for MRI sub-study protocol.

8.4.3 Study Visit(s)

If subject agrees to participate in the trial they will return to the MCRU to receive Stribild and Prezista. The subjects will take these medications for two weeks and return to be seen by the designated study staff. At this time a review of the medical history with the participant and a targeted physical exam will be performed. Blood will then be drawn for CD4, plasma, serum and PBMCs. Inguinal LN biopsy with colonoscopy with ileal and rectal biopsies will be performed. During this time blood draws will be taken at baseline and hours 1,2,3,4,6,8,12, and 24 post-drug administration. The subject will remain at the

MCRU for 12 hours for monitoring. They will then return to the MCRU the following morning for one additional blood draw at 24 hours after drug administration. They will complete the off-study form prior to discharge from the MRCU. Subjects will be instructed to report any subsequent event(s) within 3 months of study completion that the subject, or the subject's personal physician, believes might reasonably be related to participation in this study.

8.5 Schedule of Events for Additional 5 Control HIV Uninfected Subjects

Table 2. Protocol summary for HIV uninfected (control) subjects:

	Screen	Study Drug Pick-Up	MRI	Week 2
Medical history	X			
Interval medical history				X
Physical Exam ¹	X			X
Safety screening			X	
MRI			X	
Adherence counseling		X		
Pregnancy test ²	X			
HIV & HCV Ab	X			
CMP	X			X
CBC w diff	X			X
CD4 count	X			X
Serum ³				X
Plasma /PBMCs ⁴				X
Biopsies ⁵				X
PK assessment ⁶				X

1. At screening, a full physical exam will be performed. At the Week 2 visit, a targeted exam will be performed.
2. Women of childbearing age must have a negative pregnancy test prior to enrollment.
3. Serum will be used to determine levels of IL-7 and TGF-beta.
4. Plasma will be used to determine levels of cytokines and markers of inflammation. PBMCs will be used in flow cytometry and intracellular cytokine staining. Additional blood will be obtained for two-photon microscopy.
5. Inguinal LN biopsy and colonoscopy with sampling of ileal and rectal tissues.
6. Intensive 24-hour PK assessment

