5. Prior diagnosis of a chronic inflammatory disease with serologic or clinical evidence as diagnosed by a primary care physician or specialist. Examples of these include, but are not limited to, systemic lupus erythematosus, rheumatoid arthritis, scleroderma, Sjogren's syndrome, mixed connective tissue disease, psoriasis, polymyositis, dermatomyositis, vasculitis, sarcoidosis, Wegener's granulomatosis, giant cell arteritis, polyarteritis nodosa, gastrointestinal pemphigoid, eosinophilic colitis, Crohn's disease, ulcerative colitis, autoimmune hepatitis.
6. Prior diagnosis of a connective tissue disease with genetic, serologic or clinical evidence as diagnosed by a primary care physician or specialist. (Marfan's syndrome, Ehlers-Danlos syndrome).
7. Screening systolic blood pressure < 110.
8. Estimated Glomerular Filtration Rate (eGFR) of < 30ml/min/1.73 m² within 60 days of study initiation or history of advanced renal disease.
9. AST and/or ALT > 3 times the upper limit of normal within 60 days of study enrollment.
10. Potassium > 5.0 within 60 days of study enrollment.
11. Pregnancy.
12. In women of childbearing age, unwillingness to use birth control for the duration of the study.
13. Breast feeding.
14. Prior vaccination with an HPV vaccine, including Cervarix (GlaxoSmithKline) or Gardasil (Merck).
15. History of hypersensitivity or severe allergic reactions to yeast.
16. At the principle investigator's discretion if not a suitable surgical candidate.
17. Currently undergoing treatment for hepatitis C or treatment completed within the last 3 months
18. History of ≥ 3 previous inguinal lymph node biopsies

HIV-uninfected:

a. Inclusion Criteria

Participants must meet all of the following inclusion criteria to participate in this study:

1. HIV uninfected.
2. ≥ 18 years of age.
3. No contraindication to proposed study procedures.

b. Exclusion Criteria

Participants meeting any of the following exclusion criteria at baseline will be excluded from study participation:

1. Use of any immunomodulator within the 12 months prior to study enrollment (as defined above).
2. Current use of an ARB or ACEi.
3. Prior diagnosis of a chronic inflammatory disease with serologic or clinical evidence (as defined above).
4. Prior diagnosis of a connective tissue disease with genetic, serologic or clinical evidence as diagnosed by a primary care physician or specialist. (Marfan's syndrome, Ehlers-Danlos syndrome).

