7.2 Plan to Minimize Risks to Subjects

All investigators and study staff have completed required training regarding human subject protections. Study staff will comply with all related regulations and laws, included, but not limited to 45 CFR 46 and 21 CFR 50, 56 (FDA version), and HIPAA Privacy Regulations. Study will be conducted in accordance with US and international standards for good clinical practices, applicable regulations, and institutional research policies and procedures.

Subjects will be rigorously screened against inclusion/exclusion criteria to ensure that their participation is safe. All staff members responsible for taking a medical history that could potentially make the participant uncomfortable have been specifically trained for how to do this in a sensitive manner. Only qualified study or clinic staff or physicians will draw blood to minimize risks. Pregnancy testing will be performed at screening, baseline, every 3 months, and anytime during follow up when the woman or investigator suspects pregnancy. In addition, study staff will stress the importance of adherence to contraceptives in order to minimize risks related to unintended fetal exposure. Subjects will be closely observed for systemic adverse events and toxicity related to the study drug on a routine basis through interviews, clinical assessment (including measuring vital signs and physical exam), and monitoring of renal function, liver function, and hematologic panel. All lymph node biopsies will be performed by either [name], [name], or [name] who have performed >400 LN biopsies in the research setting without significant complications. All colonoscopies will be performed by [name] who has performed >300 colonoscopies and biopsies in related HIV studies in the past without any complications. Subjects will be monitored after biopsy procedures for at least 4 hours by study staff trained in managing postoperative patients. They will be monitored for at least 30 minutes after HPV vaccine administration to ensure that they tolerate the vaccine without difficulty.

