9.5 Reporting a Pregnancy

Pregnant women are not eligible to participate in the study. Women are counseled regarding prevention of pregnancy and encouraged to make every effort to avoid pregnancy during study participation. In addition to the screening and baseline visits, pregnancy testing will occur every 3 months and anytime during follow up when the woman or investigator suspects pregnancy. If a study participant becomes pregnant during study participation, no further doses of losartan or Gardasil will be given and no additional study procedures will be performed. Basic information about the pregnancy will be recorded on the "Pregnancy" CRF and permission to record survival data for her until the end of the pregnancy and of the baby at birth will be requested. If there are complications during the pregnancy, the complications are recorded as AEs in the usual way. The participant is asked to report outcome of the pregnancy. If there is a congenital anomaly in the infant, this is recorded as a serious adverse event (SAE) in the data forms for the mother (i.e., the study participant).

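### The five antiretroviral-dosed controls have their only scheduled pregnancy test at screening, while 5.2 applies the pregnancy exclusion at a baseline that 8.4 never defines

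*Combined protocol and SAP*

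**What the plan says.** Section 8.4 and Table 2 in section 8.5 govern the five additional uninfected controls, who take Stribild and Prezista for two weeks before node biopsy and colonoscopy.

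- **8.4.1 (screening):** "Women of childbearing age will have a urine pregnancy test".
- **Table 2:** four columns (Screen, Study Drug Pick-Up, MRI, Week 2). The pregnancy row is marked under Screen only. Footnote 2 reads "Women of childbearing age must have a negative pregnancy test prior to enrollment".
- **8.4.3 (drug start):** "If subject agrees to participate in the trial they will return to the MCRU to receive Stribild and Prezista". No pregnancy test is listed for this visit.
- **5.2 (uninfected list):** "Participants meeting any of the following exclusion criteria at baseline will be excluded from study participation". Pregnancy is exclusion 8 on that list.
- **7.2:** "Pregnancy testing will be performed at screening, baseline, every 3 months, and anytime during follow up when the woman or investigator suspects pregnancy". Section 9.5 repeats this calendar. Neither section says that it applies to HIV infected subjects only.
- **9.5 (if a participant becomes pregnant):** "no further doses of losartan or Gardasil will be given and no additional study procedures will be performed". Stribild and Prezista are not named.
- **9.7.2:** pregnancy is a ground for removal from the study, in a paragraph that also sets removal rules for healthy controls.

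For HIV infected women, Table 1 marks a test at screening and again at Day 0. Section 8.1.1 also ties randomisation to screening laboratory results no more than 60 days old, with a repeat chemistry panel if that lapses. Section 8.4 has no counterpart.

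**The concern.** An exclusion that applies at baseline needs a defined baseline and a way to assess it there. For the dosed controls the schedule gives a test at screening, then a return visit at which two study drugs are handed over. Nothing ties the two visits together in time, and no test is scheduled at the second. A volunteer who conceives in between could begin the two-week course undetected.

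These are healthy volunteers. Section 2.4.2 leaves controls out of the clinical laboratory results and vaccination offered to other subjects and names no other direct benefit. On paper they have less pregnancy checking before their first dose than the randomised women do. What is at stake is participant protection and whether a documented eligibility criterion can be verified, not efficacy inference.

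**Working it through.** The plan states no figure to reproduce, so the check compares the schedules with the text.

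**1. Scheduled tests up to the first dose**

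| | HIV infected (Table 1) | Dosed controls (Table 2) |
|---|---|---|
| Screening | 1 | 1 |
| Start-of-drug visit | 1 (Day 0) | 0 (Study Drug Pick-Up) |
| Tests after screening, up to first dose | 1 | 0 |
| Stated limit from screening to start | 60 days (8.1.1) | none |

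Table 2 marks 1 of its 4 columns. The 3 later contacts (pick-up, MRI, Week 2) carry no mark.

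**2. Does footnote 2 close the gap?** No. A test before enrolment is met by the screening test in 8.4.1, so footnote and table agree with each other. Table 1 carries the same footnote sentence and still marks Day 0, so the footnote was not treated there as replacing a test at the start of drug.

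**3. Does 5.2 require something later than screening?** It depends on an undefined word. The only visit headed as baseline is 8.1.2, for HIV infected subjects. Sections 8.3 and 8.4 have none. If baseline for controls means drug pick-up, no scheduled test supports the exclusion at that point. If it means screening, 5.2 and Table 2 agree. The list itself does not settle this. It ties the liver enzyme criterion to the screen and gives pregnancy no time of its own, which can be read either way.

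**4. Do 7.2 and 9.5 reach controls?** Their wording is general, and 7.2 is the plan for minimising risk to subjects overall. The quarterly calendar, however, cannot fit a two-week course.

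**5. Do other safeguards act before the first dose?**
- Testing on suspicion (7.2, 9.5) is unscheduled and needs a prompt.
- The MRI safety interview in Appendix I asks about possible pregnancy and offers kits to those unsure. It relies on self-report, and section 2.2 places the MRI during the two weeks on drug, after dosing has begun.

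**6. Number affected.** Table 2 covers 5 people. The documents do not give the sex or age mix of these controls, so the number of women concerned lies between 0 and 5. The other 5 controls (8.3) receive no study agent.

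**The case against.** The strongest reply is that there is no contradiction. Sections 7.2 and 9.5 were evidently drafted for the losartan arms: their calendar follows Table 1, and 9.5 names losartan and Gardasil. Controls are tested at screening, before enrolment, which footnote 2 requires and which satisfies 5.2 if screening is their baseline. This has force. It shows that the conflict with 7.2 and 9.5 rests on their unrestricted wording and that 5.2 is the firmer support. It does not supply a definition of baseline for controls, and it does not bound the time from the only test to the first dose.

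A reader might infer several stronger points that the documents do not support.

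- **That no rule stops dosing in a pregnant control.** Section 9.7.2 removes pregnant subjects, and 9.5 ends further study procedures for any participant. What remains is that 9.5 does not name the controls' drugs, although 9.1.8 and 9.4.2 do include them among the study agents.
- **That the baseline exclusion cannot be checked at all.** It can be, if baseline means screening.
- **That contraception is not required of controls.** Section 2.2 states it for every enrolled woman of reproductive age. Its stated reason is losartan and the uninfected list in 5.2 omits it, but the general statement exists.
- **That a test is missing before the Week 2 procedures.** Table 1 has no mark at Month 30, when the same procedures take place; its last mark is at Month 29.5. A same-visit test before procedures is not this protocol's standard.
- **That all 10 controls are exposed.** Only 5 take study drug.
- **That the plan identifies a fetal risk from these two products.** Sections 2.2 and 2.4.1 attach teratogenicity to losartan and state none for Stribild or Prezista. The point rests on the protocol's own exclusion, not on a stated drug hazard.

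**Conclusion.** The point holds in a narrow form. As scheduled, any of up to five dosed controls can start Stribild and Prezista with no pregnancy test since screening and after an interval the plan does not limit. Section 5.2 sets the exclusion at a baseline that 8.4 leaves undefined, and 7.2 and 9.5 describe a baseline test in terms that do not expressly leave controls out.

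This rests on two readings: that Table 2 and 8.4.3 give the full control schedule, and that 7.2 and 9.5 mean what their unrestricted wording says. If the second fails, the undefined baseline in 5.2 and the unlimited interval remain. Power, the randomised comparison and the analysis are unaffected. The change is worth making because it is cheap and concerns participant safety.

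**What to change.** Reconcile Table 2 and 8.4.3 with 5.2, 7.2 and 9.5. Either of two routes makes the text consistent:

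1. State which control visit is baseline, and show in Table 2 and 8.4.3 the baseline test that 7.2 and 9.5 describe; or
2. Limit 7.2 and 9.5 expressly to HIV infected subjects, and state that the 5.2 exclusions are assessed at screening for controls.

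The second route makes the documents agree but leaves the interval from screening to first dose as it is, so the sponsor should choose it knowingly. The choice between them is a clinical decision for the sponsor and investigators.

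Separately, and as wording only, align the 9.5 sentence that names losartan and Gardasil with 9.7.2 and with the control agents in 6.1.3 and 6.1.4.

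The cost is a few text and table edits. Under the first route there is also at most one urine test per person, for up to five people; if the visit named is drug pick-up, that visit already exists.

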9. ASSESSMENT OF SAFETY

9.1 Definition of an Adverse Event (AE)

9.1.1 Basic Definition

An AE is any symptom, sign, illness, or experience that develops or worsens in severity during the course of the study but does not necessarily have a causal relationship with a study agent/intervention or procedure. An AE can therefore be any unfavorable and unintended sign (including an abnormal laboratory finding), symptom, or disease temporally associated with the use of the study agent/intervention or procedures whether or not it is related to the study agent/intervention. Intercurrent

illnesses or injuries will be regarded as AEs. Abnormal results of diagnostic procedures are considered to be AEs if the abnormality:

- results in study withdrawal,
- is associated with a serious adverse event (SAE),
- is associated with clinical signs or symptoms,
- leads to additional treatment or to further diagnostic tests, or
- is considered by the Investigator to be of clinical significance.

9.1.2 Definition of a Serious Adverse Event (SAE)

Adverse events are classified as serious or non-serious. An SAE is any AE that is:

- Fatal,
- life-threatening,
- requires or prolongs a hospital stay,
- results in persistent or significant disability or incapacity,
- a congenital anomaly or birth defect, or
- an important medical event.

Important medical events are those that may not be immediately life threatening, but are clearly of major clinical significance. They may jeopardize the subject, and may require intervention to prevent one of the other serious outcomes noted above. For example, drug overdose or abuse, a seizure that did not result in inpatient hospitalization, or intensive treatment of bronchospasm in an emergency department would typically be considered serious. All AEs that do not meet any of the criteria for serious should be regarded as non-serious AEs.

9.1.3 Definition of a Suspected Unexpected Serious Adverse Reaction (SUSAR)

An AE that is:

- Serious (i.e., an SAE),
- Related (i.e., there is a reasonable possibility that the AE may be related to the study product), and
- Unexpected (i.e., an AE whose nature or severity [intensity] is not consistent with the applicable product information found in an investigator's brochure, a package insert or a summary of agent characteristics).

9.1.4 Preexisting Condition

A preexisting condition is one that is present at the start of the study. A preexisting condition will be recorded as an AE if the frequency, intensity, or character of the condition worsens during the study period.

9.1.5 Post-study Adverse Event

All unresolved AEs will be followed by the Investigator until the events are resolved, the subject is lost to follow-up, or the AE is otherwise explained. At the last scheduled visit, the Investigator will instruct each subject to report any subsequent event(s) within 3 months of study completion that the subject, or the subject's personal physician, believes might reasonably be related to participation in this study.

9.1.6 Abnormal Laboratory Values

A clinical laboratory abnormality should be documented as an AE if any 1 of the following conditions is met:

- The laboratory abnormality is not otherwise refuted by a repeat test to confirm the abnormality,

- The abnormality suggests a disease and/or organ toxicity, or
- The abnormality is of a degree that requires active management; e.g., change of dose, discontinuation of the drug, more frequent follow-up assessments, further diagnostic investigation, etc.

9.1.7 Hospitalization, Prolonged Hospitalization, or Surgery

Any AE that results in hospitalization or prolonged hospitalization will be documented and reported as a SAE unless specifically instructed otherwise in this protocol. Any condition responsible for surgery should be documented as an AE if the condition meets the criteria for an AE.

Neither the condition, nor hospitalization, nor prolonged hospitalization, nor surgery are reported as an AE in the following circumstances:

- Hospitalization or prolonged hospitalization for diagnostic or elective surgical procedures for a preexisting condition. Surgery should not be reported as an outcome of an AE if the purpose of the surgery was elective or diagnostic and the outcome was uneventful.
- Hospitalization or prolonged hospitalization required to allow efficacy measurement for the study.
- Hospitalization or prolonged hospitalization for therapy of the target disease of the study, unless it is a worsening or increase in frequency of hospital admissions as judged by the clinical Investigator.

9.1.8 Anticipated Adverse Events

AEs are not anticipated, but there are AEs associated with the use of both study agents and with the procedures being performed in the study. Possible AEs are described above in section 7.1 above and in consent forms. Plans to minimize the occurrence of these AEs are described in section 7.2 above. We do not expect any serious adverse events due to losartan, Stribild, Prezista, or Gardasil use or from any of the study procedures.

9.2 Unanticipated Problems

Unanticipated problems (UP), as defined by the OHRP include any incident, experience, or outcome that meets **all** of the following criteria:

1. Unexpected (in terms of nature, severity, or frequency) given (a) the research procedures that are described in the protocol-related documents, such as the IRB-approved research protocol and informed consent document; and (b) the characteristics of the subject population being studied;
2. Related or possibly related to participation in the research (in this guidance document, “possibly related” means there is a reasonable possibility that the incident, experience, or outcome may have been caused by the procedures involved in the research); and
3. Suggests that the research places subjects or others at a greater risk of harm (including physical, psychological, economic, or social harm) than was previously known or recognized.

Upon becoming aware of any AE, the PI will assess whether the AE represents an unanticipated problem by applying the criteria described above. If the PI determines that the AE represents an unanticipated problem, the PI will report it promptly to the University of Minnesota IRB and DSMB within their reporting timelines. In addition, incidents, experiences and outcomes that occur during the conduct of this study that represent unanticipated problems but are not considered AEs may require reporting under the HHS regulations at 45

CFR 46.103(a) and 46.103(b)(5). Further details and examples of such scenarios are described in the OHRP policy (<http://www.hhs.gov/ohrp/policy/advevntguid.html#Q1>). Unanticipated problems involving risks to participants or others will be reported as detailed in the DAIDS Critical Event Policy (<http://www.niaid.nih.gov/LabsAndResources/resources/DAIDSClinRsrch/Pages/Safety.aspx>).

